7.2.2 Secondary Aims

Continuous secondary outcomes, including change in systolic and diastolic blood pressure and change in HbA1c, QOL questionnaires such as the SF-36, PHQ-9, and eating behavior scores will be compared between treatment arms using ANCOVA with adjustment for the same variables specified in the primary analysis.

Binary outcomes, including proportion with $\geq 25\%$ reduction in %EWL and incidence of esophagitis will be compared between treatment arms by Pearson Chi-square test.

Among patients randomized to the treatment ESG group, the association between the durability of plication at repeat endoscopy (score ≥ 1 on EGD grading system) and number of sutures required for re-tightening with change in EWL from 12 months to 24 months will be assessed using linear regression with adjustment for BMI, %EWL between randomization and 12 month follow up, HTN status, and DM status. This is an observational comparison.

Among patients randomized to the control LS arm, the percent EWL from the 12 month assessment to the 24 month assessment will be measured. This percentage will be compared to percent EWL in the same group with lifestyle intervention only in the first 12 months using a one sample t-test.

Among all subjects, %EWL will be compared at 24 months between initial and delayed ESG. However, this is not considered a comparison of randomized arms as follow up is not continued for patients with $\geq 25\%$ EWL from LS at 12 months.

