7 STATISTICAL ANALYSIS

7.1 Power and Sample Size

The primary endpoint for power and sample size is %EWL at 12 months. The null hypothesis is no difference in mean %EWL between ESG and LS randomized arms ($H_0: \mu_t = \mu_c$ where μ_t is the average %EWL in the ESG group and μ_c is average %EWL in the LS group). We will perform a two-sided hypothesis test at alpha level 0.05 (alternative hypothesis $H_a: \mu_t \neq \mu_c$) Based on the published literature with the ESG technique a conservative presumption is 25% EWL in the ESG arm with a standard deviation (SD) of 30% at 12 months compared to 10% EWL on LS alone with SD of 5%. We plan a 1:1.5 randomization scheme that allocates 3 patients to LS for every 2 to ESG at the time of randomization. Based on a two-sample t-test with unequal variances and two-sided alpha=0.05, we would have 80% power to detect a difference of 15% in average %EWL between groups with 34 patients allocated to ESG and 51 randomized to LS. 90% power would require group sizes of 45 and 68, respectively. To allow for dropout, and more importantly, to power exploratory aims for obesity comorbidity subgroups, we propose the initial randomization of 200 patients – 80 to ESG and 120 to LS.

120 subjects are initially randomized to LS in level 1. Of these, we anticipate up to 20% will achieve a successful decrease of $\geq 25\%$ in %EWL through LS alone at 12 months. Further, we anticipate up to 20% may be lost to follow up or drop out prior to 12 month follow up. Thus, we anticipate at least 77 ($120 * 0.8 * 0.8$) subjects to continue to level 2 and be offered ESG. We will test the one-sample hypothesis (non-randomized) that of those offered ESG at 12 months, average change in %EWL will be at least 10%. Based on a one-sample t-test with two-sided alpha=0.05 and standard deviation at 24 months of 30%, 70 subjects completing ESG would have 98% power to detect an effect of 25% reduction in %EWL.

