7.2.3 Secondary Analyses

A per-protocol analysis will compare ESG to LS randomized groups among protocol adherent patients – here, defined among ESG randomized patients as those actually receiving the procedure and making $\geq 80\%$ follow-up visit in both treatment and control groups. Modified ITT will be considered the primary approach for all efficacy analyses, and will include patients who actually receive the ESG or started the life-style program regardless of adherence to follow-up visits. Safety endpoints and adverse events may be evaluated based on treated group (per-protocol).

Additional analyses may assess the moderating effect of HTN and DM on the effect of ESG vs LS at 12 months. Linear regression will include an interaction between HTN (or DM) and randomized group to determine the effect of ESG in subgroups and whether the effect is different between HTN and non-HTN (also, separately, DM and non-DM) patients.

Additional outcomes and analyses not specified here are considered exploratory and post-hoc and will be clearly identified as such in any publications.

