7.3 Missing Data

The primary analysis uses a hierarchical regression model, assuming post-randomization dropout is missing at random (MAR) among subjects completing at least 1 of the 11 planned follow up visits.

Patients excluded after randomization and before ESG/LS on the basis of identified exclusion criteria will be excluded from analyses; reasons for meeting exclusion criteria will be documented. Patients that withdraw/dropout between randomization and ESG/LS are assumed to be missing completely at random. However, a sensitivity analysis will compare withdrawn subjects to participating subjects and perform analyses under MAR (including multiple imputation) assumptions if these subjects appear different or if dropout occurs at substantially different rate in one arm compared to the other. Participating patients who dropout prior to the first follow up visit will be analyzed similarly.

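### Section 7.2.2 analyses continuous secondary outcomes by ANCOVA with no visit term and no missing-data rule, so by default patients lost after the first follow-up visit contribute nothing, although interim values are collected

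*Combined protocol and SAP*

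**What the plan says.** Section 7.2.1 fits a hierarchical model to %EWL at 11 post-randomization timepoints and reads the arm contrast off at 12 months. Section 7.3 gives the matching missing-data assumption: "The primary analysis uses a hierarchical regression model, assuming post-randomization dropout is missing at random (MAR"), for anyone with at least one follow-up visit.

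Section 7.2.2 changes method. Continuous secondary outcomes, with blood pressure, HbA1c, SF-36, PHQ-9 and eating behavior as named examples, "will be compared between treatment arms using ANCOVA with adjustment for the same variables specified in the primary analysis". Those variables are age, sex, baseline BMI, HTN and DM. No visit term is given, the outcome's own baseline value is not listed, and nothing is said about a missing 12-month value. Section 4.2.1 sets 12 months for blood pressure and HbA1c; for the questionnaires it follows from the opening of section 7.2.

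For the optional moderation analysis, section 7.2.3 says: "Linear regression will include an interaction between HTN (or DM) and randomized group". The outcome is not named.

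Multiple imputation appears in section 7.3 only as a conditional sensitivity analysis, for people who leave before ESG or lifestyle starts or before the first follow-up visit. Section 7.2.3 makes modified ITT the primary approach for all efficacy analyses and keeps patients in whether or not they attend follow-up.

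The year 1 schedules in section 5.6 mark weight and vital signs at every clinic visit, and IWQOL-Lite, SF-36, PHQ-9 and TFEQ at baseline and weeks 12, 24 and 52, in both arms. Laboratory tests differ: ESG patients have baseline, week 24 and week 52; controls have baseline and week 52 only.

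**The concern.** An ANCOVA of a single 12-month value uses only patients who have that value, unless a rule says otherwise, and none does. A patient seen through week 48 and then lost would count in the %EWL analysis but not in the blood pressure or quality-of-life analysis. That falls short of the plan's own modified ITT set.

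Two things are at stake. One is precision: section 7.1 says of the lifestyle arm that "we anticipate up to 20% may be lost to follow up or drop out prior to 12 month follow up", and it enlarges the trial to 200 chiefly for the comorbidity subgroups. The other is bias: the trial is open-label, and if patients leave one arm because of how they are doing, completers no longer represent that arm. The interim readings would correct this under missing at random, but the planned analysis does not use them.

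If %TBWL also goes to ANCOVA, it and %EWL would be estimated on different patients from the same weights.

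**Working it through.** **1. The plan's own figure.** Section 7.1 assumes "25% EWL in the ESG arm with a standard deviation (SD) of 30% at 12 months compared to 10% EWL on LS alone", with SD 5 in the lifestyle arm, and a Welch t-test at two-sided alpha 0.05. At 34/51, SE = √(900/34 + 25/51) = 5.19 and 15/5.19 = 2.89; the noncentral t with 34.2 df gives 80.2% power (stated 80%). At 45/68 it gives 90.2% (stated 90%). Both reproduce. After 20% loss in both arms (64/96) the same test has 97.4% power, so primary power is not the issue. The plan states no power or missing-data figure for the ANCOVAs.

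**2. Cost of losing 20%.** Applying 20% to ESG as well is an assumption. Detectable difference at 80% power = (1.960 + 0.842) × √(1/n₁ + 1/n₂), in SD units:

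- 80/120: 2.802 × 0.1443 = 0.404
- 64/96: 2.802 × 0.1614 = 0.452
- a 50-patient comorbidity group, 20/30 falling to 16/24: 0.81 rising to 0.90

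For a true 0.404 SD effect, completer power is Φ(0.404/0.1614 − 1.96) = 70.7%, against 80% with no loss.

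**3. What interim data could recover.** With loss d = 0.2, one interim value on everyone and visit correlation ρ, the repeated-measures variance relative to no loss is (1 − ρ²)/(1 − d) + ρ²; for completers it is 1/(1 − d) = 1.25. The documents give no ρ.

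- ρ = 0.5: 0.75/0.8 + 0.25 = 1.1875, a ratio of 0.95
- ρ = 0.7: 0.51/0.8 + 0.49 = 1.1275, a ratio of 0.90
- ρ = 0.9: 0.19/0.8 + 0.81 = 1.0475, a ratio of 0.84

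This formula ignores the baseline value. Baseline adjustment already captures much of the same information, so step 4 includes it.

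**4. Baseline-adjusted simulation.** Assumptions: 80/120; baseline and weeks 12, 24 and 52; true effect −0.404 SD; all loss after week 24; 2,000 trials per scenario. In the outcome-related scenarios, the odds of leaving rise with a poor week-24 change. Ranges are over ρ = 0.5, 0.7 and 0.9; RM is the repeated-measures estimate.

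| Loss, ESG/lifestyle | Bias, completer ANCOVA | Bias, RM | Variance ratio, RM/ANCOVA |
|---|---|---|---|
| 20/20, random | −0.002 to 0.002 | −0.003 to 0.003 | 0.946–0.972 |
| 20/20, outcome-related, same in both arms | −0.004 to 0.002 | −0.003 to 0.002 | 0.926–0.959 |
| 10/30, outcome-related | 0.030 to 0.048 | −0.002 to 0.004 | 0.932–0.983 |
| 10/30, strongly outcome-related | 0.046 to 0.067 | −0.001 to 0.002 | 0.953–0.970 |

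The bias at 10/30 is 0.030/0.404 = 7% to 0.067/0.404 = 17%, toward the null. The extra ANCOVA variance is 1/0.983 − 1 = 2% to 1/0.926 − 1 = 8%.

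**5. Other dropout and correlation assumptions.** Further simulations (true effect −0.40 SD, outcome-related loss in the lifestyle arm only, odds of leaving × 2.7 per SD, constant and serially decaying correlations) gave −0.30 to −0.36 for baseline-adjusted ANCOVA: 0.04/0.40 to 0.10/0.40, or 10–25% lost. With lifestyle loss held at 18–19%, within the plan's expectation, the estimates were −0.32 to −0.37: 0.03/0.40 to 0.08/0.40, or about 8–20%. With the same mechanism in both arms they were −0.39 to −0.41. Across all runs the extra variance was roughly 2–10%.

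**6. In power terms.** If completer ANCOVA has 70.7% power, a model with 2–10% less variance inflation has Φ(2.504 × √1.02 − 1.96) = 71.5% to Φ(2.504 × √1.10 − 1.96) = 74.7%. The precision gain is modest.

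**The case against.** The strongest reply is that baseline-adjusted ANCOVA at a fixed timepoint is a standard secondary analysis, that the precision gain is small, and that bias needs outcome-related loss concentrated in one arm. All of that stands. The one-arm assumption is also open to challenge: under section 5.5.1.1.1, controls who attend at least 75% of visits and have not reached 25% EWL, or still have BMI 30–40, can cross over to ESG. That gives poor responders a reason to stay, at least as regards weight. It also makes attendance incentives differ between arms, so the direction of any bias cannot be predicted.

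Four stronger readings are tempting, and the documents do not support them.

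- *The plan discards every dropout.* It does not say so. Complete-case analysis is the default consequence of the method, and section 7.3 allows conditional imputation for those who leave before intervention or before the first visit.
- *Some 28–50% of the effect is lost, with 14–25% more variance.* Those figures come from an unadjusted week-52 difference with no baseline outcome term. They should not be quoted for ANCOVA.
- *The HTN/DM moderation analysis uses only the 12-month value.* Section 7.2.3 is ambiguous. Section 7.2.1 also describes linear regression with a 12-month comparison, yet uses all visits. The analysis is optional and %EWL as its outcome is inferred.
- *%TBWL is assigned to ANCOVA.* Section 7.2.2 does not name it; this is inferred from an open-ended list.

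**Conclusion.** The point holds, at moderate size. The plan has no rule for a patient with interim secondary data but no 12-month value, although the data and a suitable model are both already in the plan.

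With about 20% loss, completer ANCOVA has roughly 2–10% more variance than a repeated-measures model. Its bias is roughly 7–25% of a 0.4 SD effect if outcome-related loss falls mainly on one arm, and immaterial if the mechanism is the same in both.

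These sizes rest on assumed visit correlations and dropout mechanisms, on 20% loss applying to ESG too in the variance calculation, and on one-arm bias scenarios some of which put lifestyle loss above the 20% the plan expects. They also read ANCOVA as including the outcome's own baseline, which section 7.2.2 does not list. For %TBWL, which is zero at baseline by definition, the baseline-adjusted range is less secure. The primary analysis is unaffected.

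**What to change.** In section 7.2.2, replace the ANCOVA by the primary-type mixed model (treatment by visit, week-52 contrast, primary covariates plus the baseline value of the outcome):

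- SBP, DBP and %TBWL: all visits. For %TBWL, baseline BMI is already a covariate and there is no separate baseline value to add.
- IWQOL-Lite, SF-36, PHQ-9 and TFEQ: weeks 12, 24 and 52.
- HbA1c: keep ANCOVA, because controls have no interim value, with multiple imputation using baseline HbA1c and the weight trajectory.

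In section 7.2.3, if the optional HTN/DM moderation analysis of %EWL is done, fit the interaction within the primary mixed model. In section 7.3, extend the missing-at-random statement to these analyses.

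The cost is SAP wording and a little more programming, with no new data. The secondary results would then rely on missing at random, as the primary result already does.

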4.2 Endpoints

4.2.1 Effectiveness

Primary:

- % EWL at 12 months from randomization by randomized arm measured at the week 52 visit. The null hypothesis is no difference in mean %EWL between randomized arms.

Secondary:

- Proportion with $\geq 25\%$ EWL at 12 months by randomized arm
- Change in hypertension in the ESG group compared to LS only

- Proportion of patients off or with reduction in their antihypertensive medications in the randomized control arm compared to lifestyle control at 12 months
- Change in systolic and diastolic blood pressure in the randomized arm compared to lifestyle control at 12 months
- Comparing diastolic and systolic blood pressures as continuous variables 12 months after ESG (compared to baseline) in the entire cohort that received ESG both in the randomized and cross-over segments of the trial
- Change in type II diabetes in the ESG groups compared to LS only
 - Proportion of patients off or with reduction in their diabetes medications in the randomized arm compared to lifestyle control at 12 months
 - Change in HgbA1c in the randomized arm compared to lifestyle control at 12 months
 - Comparing HgbA1c as a continues variable 12 months after ESG (compared to before) in the entire cohort that received ESG both in the randomized and cross-over segments of the trial.
- %TBWL in the ESG group compared to LS only
- % of patients in the ESG group achieving > 5% TBWL compared to LS only
- % of patients in the ESG group achieving > 10% TBWL compared to LS only
- Durability of the plication evaluated by endoscopy at 12 months (level 1) and effectiveness of re-tightening procedure performed at 12 months (level 1) in maintaining and / or enhancing weight loss at 24 months. Durability of the plication and procedure is defined as greater than 70% of the cohort undergoing repeat endoscopy achieving a score of ≥ 1 out of 3 prior to re-tightening (Grading system and evaluation in appendix). Efficacy of re-tightening is defined as $\geq 50\%$ of the cohort undergoing the re-tightening maintaining or losing weight compared to the re-tightening weight at 12 months after the re-tightening procedure.
- Incidence of esophagitis at repeat endoscopy at 12 months (level 1). (LA grading system in form in appendix)
- Changes in quality of life assessed using standard validated questionnaires (IWQOL-lite and SF-36)
- Changes in depression assessed using PHQ-9 questionnaire

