5.3 Screening and Eligibility Assessment

Screening will be conducted by the investigator or the co-investigator and documented on the Investigator delegated/medically qualified team member intake form (conventionally known as PI Intake Form) (Appendix A) and Screening Labs form (Appendix B). Screening must occur no more than 45 days prior to randomization.

Screening will include the following:

1. Sign informed consent form
2. Screening exam and intake by the investigator or co-investigator
3. Height, weight and BMI; waist and hip circumference; vital signs (blood pressure and pulse)
4. Dietary screening intake and approval
5. Laboratory tests (after 8 hours fasting)

- **CBC:** Hgb, Hct, WBC, MCV, platelets
- **Chemistry panel:** sodium, potassium, chloride, CO₂, BUN, creatinine, fasting glucose, insulin, SGOT/AST, SGPT/ALT, alkaline phosphatase, total bilirubin, direct bilirubin, total protein, albumin, fasting lipids profile (total cholesterol, triglyceride, LDL cholesterol, HDL cholesterol) Fe/TIBC, iron, B12, 25-Hydroxy Vitamin D, TSH, total Ghrelin level (only if available at participating institution), C-reactive protein.
- **Coag:** Pro Time or INR, PTT
- **PYY-1, GLP-1, Total Ghrelin** pending sites' availability to analyze
- **Urinalysis**
- **HgbA1C**
- **H. Pylori Breath Test.** **Patients with a positive h-pylori breath test will be treated and eradication must be confirmed with a stool antigen after treatment and prior to randomization**
- **EKG** for patients 50 years old or older
- **Urine pregnancy test** for women of child bearing potential

6. Questionnaires
7. Psychological evaluation and approval: Study psychologists will use their standard clinical evaluations for bariatric interventions.

Within one week of completion of the screening tests, the PI will review the results and determine the participant's eligibility. The center will inform the participant of their screening results within 10 days of completing testing. Any abnormal lab results will be communicated to the participant and they will be required to notify their primary care provider for any further action that may be necessary. All potential participants who qualify for randomization based on the initial screening assessments will return for a randomization visit where participants will have the chance to review any questions with the study staff, as well as a recap of the follow-up schedule, and they will then receive their randomization assignment.

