5.6 Schedule of Events

5.6.1.1 Schedule of Events for Treatment Group, Year 1, Level 1

TABLE 1. MERIT SCHEDULE OF EVENTS (Year 1, Level 1, Treatment Group, 80 patients)											
	Enrollment; Screening/ Baseline	Randomization	ESG Procedure	Post-Op Phone Call	Weeks 1, 4, 8	Week 12	Weeks 16, 20	Week 24 (6 month)	Weeks 30, 36, 42, 48	Week 52 (Final Year 1 visit)	Unscheduled Visit
Visit Number	-1		0	-	1,2,3	4	5,6	7	8,9,10,11	12	
Informed consent	X										
Complete Physical Exam (CPE) by Investigator or Investigator delegated / medically qualified team member	X					X		X	X	X	X
Investigator or Investigator delegated/medically qualified team member exam					X	X	X	X	X	X	X
EKG if (> 50 yo)	X										
Formal nutritional assessment	X										
Formal psychology evaluation	X										
Pregnancy test (females of childbearing potential only)	X										
Laboratory tests, H-pylori breath testing (baseline only)**	X							X		X	
Questionnaires#	X					X		X		X	
Inclusion/exclusion criteria	X										
Endoscopy / Procedure			X								
Procedure Assessment Form			X								
GERD Questionnaire + Activity Assessment Form	X				X	X	X	X	X	X	
Weight, BMI/height, Waist and Hip Circumference Form	X		X		X	X	X	X	X	X	X
Vital Signs Form	X		X		X	X	X	X	X	X	X
Adverse Events Form			X	X	X	X	X	X	X	X	X
Medications Form##	X		X	X	X	X	X	X	X	X	X
Post-enrollment Nutrition / Exercise / satiety counseling and assessment		X++			X	X	X	X	X	X	
Randomization to ESG+	X	X									
Subject Satisfaction Questionnaire (treatment phase)										X	

** Electrolytes, Creatinine, CBC, Iron, TIBC, B12, 25-hydroxy Vitamin D, TSH, HgA1c, fasting blood sugar and insulin, PTT, fasting lipids profile (total cholesterol, LDL, HDL, and Triglyceride), ALT, AST, ALK-P, total bilirubin, direct bilirubin, BUN, total protein, albumin, CRP, urinalysis; also include PY-Y-1, GLP-1 and total Ghrelin pending sites' availability to analyze

Eating disorder questionnaire + hospital anxiety and depression questionnaires (only at base-line), IWFQOL-Lite, SF36, PHQ9, Pittsburgh Sleep Quality Index (PSQI), Three factor eating questionnaire (TFEQ)

Record all medications including dose and frequency; especially diabetes and blood pressure medication.

+ To occur after all screening assessments are complete; within 45 days of screening evaluations

++ Nutritional visit to discuss upcoming post-op liquid diet

5.6.1.1.2 Schedule of Events for Treatment Group, Year 2, Level 2

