7.2.1 Primary Aim

The primary outcome is %EWL at 12 months assessed in the two randomized arms. A hierarchical linear regression model will be fitted to post-randomization %EWL measurements, planned for 11 post-randomization timepoints through 12 months. Post-randomization outcomes will be modeled as a function of discrete visit (instead of assuming a linear or other functional form of time since randomization) and treatment indicator variables. Models will also adjust for age, sex, baseline BMI, HTN, and DM status to reduce residual variation and improve power. The primary outcome comparison at 12 months is estimated from a linear combination of treatment and time indicators. A spatial autocorrelation covariance structure will be used.

Assumptions for normality of residuals and homoscedastic variance will be assessed; hierarchical median regression (Geraci and Bottai, 2014) will be considered under significant violations.

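### The secondary ANCOVAs for blood pressure, HbA1c and questionnaire scores reuse the %EWL covariate list and so leave out each outcome's own baseline value, giving up precision.

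*Combined protocol and SAP*

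**What the plan says.** Section 7.2.2 names the outcomes concerned as "change in systolic and diastolic blood pressure and change in HbA1c, QOL questionnaires such as the SF-36, PHQ-9, and eating behavior scores". It states that they will be "compared between treatment arms using ANCOVA with adjustment for the same variables specified in the primary analysis". The list it refers to is in section 7.2.1: "Models will also adjust for age, sex, baseline BMI, HTN, and DM status to reduce residual variation and improve power".

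Section 4.2.1 frames these endpoints as changes, for example "Change in HgbA1c in the randomized arm compared to lifestyle control at 12 months" and "Changes in quality of life assessed using standard validated questionnaires (IWQOL-lite and SF-36". Section 7.2.2 uses the word change for blood pressure and HbA1c, but does not say whether the questionnaires enter as change or as 12-month scores.

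The baselines are scheduled. Section 5.3 has blood pressure and HbA1c at screening. The year 1 tables in section 5.6 mark the questionnaires (IWQOL-Lite, SF-36, PHQ-9 and TFEQ among them) at screening/baseline in both arms. No section names any of these baseline values as a covariate.

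**The concern.** The covariate list was written for %EWL, which is zero at baseline by construction and so has no baseline value to adjust for. Blood pressure, HbA1c and the questionnaires do have one, and it is usually the covariate that explains most of the 12-month value. Hypertension status, diabetes status and baseline BMI are only proxies for it. Read literally, the plan compares change scores with proxy covariates. This falls short of the purpose that 7.2.1 itself gives for adjustment, which is to reduce residual variation and gain power.

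These models supply the randomized continuous evidence on blood pressure and HbA1c for Objective 2. If the baseline is left out, the estimates are less precise than the collected data allow, because a share of any chance baseline difference between arms stays in them. There is also a procedural cost. Section 7.2.3 classes analyses that were not specified as exploratory and post hoc, so a baseline-adjusted model added later could fall under that label. Leaving the point open would also allow a choice between two models after the data are seen.

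**Working it through.** **The plan's own figures.** The only power figures for the randomized comparison are those for %EWL in section 7.1. A Welch t-test (means 25 and 10, SDs 30 and 5, two-sided alpha 0.05) gives 80.1% power at 34/51 and 90.2% at 45/68, so the stated 80% and 90% reproduce. The plan gives no SD, correlation or power for the secondary ANCOVAs.

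**Inputs**
- From section 7.1: 80 ESG and 120 lifestyle patients; up to 20% dropout, stated for the lifestyle arm and applied here to both arms (64/96).
- Assumed, not in the documents: baseline-to-12-month correlation r = 0.5 to 0.7; equal variance s² at both times; SBP SD 15 mmHg; hypertension and diabetes status explain a share q of baseline variance and act on follow-up only through baseline. q = 0 is plausible for questionnaires, and 0.2 to 0.4 for blood pressure and HbA1c.

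**Residual variance of a change score**
- As written: s²[(1−r)²(1−q) + (1−r²)]
- With the outcome's baseline added: s²(1−r²)
- Ratio: 1 + (1−r)(1−q)/(1+r)

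For example, r = 0.5 and q = 0 gives 1 + 0.5/1.5 = 1.333. The equivalent sample loss is 1 − 1/ratio.

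| r | q | Ratio | Simulated ratio | Equivalent sample loss |
|---|---|---|---|---|
| 0.5 | 0 | 1.333 | 1.335 | 25% |
| 0.5 | 0.2 | 1.267 | 1.261 | 21% |
| 0.5 | 0.4 | 1.200 | 1.198 | 17% |
| 0.7 | 0 | 1.176 | 1.165 | 15% |
| 0.7 | 0.2 | 1.141 | 1.124 | 12% |
| 0.7 | 0.4 | 1.106 | 1.097 | 10% |

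The simulation used 80/120 patients, three strata and 20,000 runs.

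**Power.** At q = 0, a change-score analysis with 80% power would have Φ(2.80·√ratio − 1.96) with the baseline added: 89.9% at r = 0.5 and 86.0% at r = 0.7.

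**Detectable SBP difference at 80% power** = 2.80 × 15 × √(1/n₁+1/n₂) × √(residual variance/s²). At 80/120, 15 × √(1/80+1/120) = 2.17 mmHg; at 64/96, 15 × √(1/64+1/96) = 2.42 mmHg.

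| n | r | As written, q = 0 | As written, q = 0.4 | With baseline |
|---|---|---|---|---|
| 80/120 | 0.5 | 6.07 | 5.75 | 5.25 |
| 80/120 | 0.7 | 4.70 | 4.56 | 4.33 |
| 64/96 | 0.5 | 6.78 | 6.43 | 5.87 |

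**The same effect seen as imbalance.** A chance SBP imbalance of one standard error (2.17 mmHg at 80/120) shifts the estimate by (1−r) × 2.17 × √(1−q): 1.08 mmHg at r = 0.5 and q = 0, 0.84 at r = 0.5 and q = 0.4, and 0.65 at r = 0.7 and q = 0. This is the source of the lost precision, not a second loss to add to it.

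**If questionnaires are analysed as 12-month scores**, the ratio without the baseline (q = 0) is 1/(1−r²): 1.33 at r = 0.5 and 1.96 at r = 0.7.

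**Cost of the extra covariate.** Seven parameters (intercept, arm, five covariates) become eight. The variance rises by about (N−8)/(N−9): 192/191, or 0.5%, at N = 200; 152/151, or 0.7%, at N = 160; and 42/41, or 2.4%, at N = 50.

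**The case against.** The best counter-argument is that ANCOVA on an outcome with a baseline is commonly taken to include that baseline. The plan does not say that only the listed variables will be used. Baseline BMI also serves as a starting-weight measure for %EWL, so the authors may have meant each outcome's baseline to take that role. This is possible, and the documents do not rule it out. Against it, the text calls for the same variables, the list is explicit, and a programmer following it would leave the baseline out. Elsewhere in 7.2.2, where a prior outcome value is wanted (the regression of 12-to-24-month weight change on plication durability), it is written out. If baseline adjustment was intended, the added words only confirm it.

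The size is also open to challenge, and part of that stands. Neither r, q nor the SD is in the documents, and the loss can be small. If diabetes status explained 60% of baseline HbA1c variance and r were 0.7, the ratio would be 1 + 0.3 × 0.4/1.7 = 1.07.

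The analysis population is unclear as well, because section 4.2.1 lists the blood pressure and HbA1c endpoints under hypertension and diabetes. If each were restricted to a comorbidity group at the quota of 50 (about 20/30), the 80/120 figures would not apply. At r = 0.5 the detectable difference would be 0.81 SD without the baseline and 0.70 SD with it. This changes the scale, but the direction is the same.

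**Conclusion.** The concern holds. As written, the continuous secondary models omit the outcome's own baseline, although it is collected in both arms. For change scores at r = 0.5 to 0.7 and q = 0 to 0.4, the variance is 11% to 33% larger than it need be. The ratio depends on assumed correlations, so it should be read as a range; every setting tried showed a loss. The effect is limited to precision in secondary endpoints. The estimates remain unbiased on average, and the primary %EWL analysis, the sample size and the medication-reduction endpoints are untouched. No stated power claim is falsified. It is a modest defect, but worth correcting before analysis because the remedy is so cheap.

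**What to change.** In section 7.2.2, after the reference to the primary-analysis variables, add: *plus the baseline value of the outcome analysed*. Apply this to SBP, DBP, HbA1c and the questionnaire scores measured at baseline (SF-36, PHQ-9, TFEQ, IWQOL-Lite), and keep the existing covariates. It does not apply to %EWL or %TBWL, which are zero at baseline.

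In the same edit, state whether the questionnaires are analysed as change or as 12-month scores, and whether the blood pressure and HbA1c models use all randomized patients or only those with the comorbidity. Once the baseline is in the model, the change and 12-month forms give the same treatment estimate, so the first choice affects only presentation.

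The cost is a line or two of SAP wording and one degree of freedom per model. No new data, visits or patients are needed.
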